The Human Subjects Division (HSD) strives to ensure that people with disabilities have access to all services and content. **If you experience any accessibility-related issues with this form or any aspect of the application process, email [contact] for assistance.**

INSTRUCTIONS

- **This form is only for studies that will be reviewed by the UW IRB.** Before completing this form, check [HSD's website](#) to confirm that this should not be reviewed by an external (non-UW) IRB.
- **If you are requesting a determination** about whether the planned activity is human subjects research or qualifies for exempt status, you may skip all questions except those marked with **[DETERMINATION]**. For example **1.1. [DETERMINATION]** must be answered. Do not upload consent materials for determinations in **Zipline** as HSD does not review or approve them.
- **Answer all questions.** If a question is not applicable to the research or if you believe you have already answered a question elsewhere in the application, state "NA" (and if applicable, refer to the question where you provided the information). If you do not answer a question, the IRB does not know whether the question was overlooked or whether it is not applicable. This may result in unnecessary "back and forth" for clarification. Use non-technical language as much as possible.
- For collaborative or multi-site research, describe only the UW activities unless you are requesting that the UW IRB provide the review and oversight for non-UW collaborators or co-investigators as well.
- You may reference other documents (such as a grant application) if they provide the requested information in non-technical language. Be sure to provide the document name, page(s), and specific sections, and upload it to **Zipline**. Also, describe any changes that may have occurred since the document was written (for example, changes that you've made during or after the grant review process). In some cases, you may need to provide additional details in the answer space as well as referencing a document.
- **NOTE: Do not convert this Word document to PDF.** The ability to use "tracked changes" is required in order to modify your study and respond to screening requests

INDEX

- | | | |
|--|--|---|
| 1. Overview | 6. Children (Minors) and Parental Permission | 11. Economic Burden to Participants |
| 2. Participants | 7. Assent of Children (Minors) | 12. Resources |

1. OVERVIEW

Study Title:

Clinical trial using an insulin dosing calculator on hospital admission

- 1.1. **[DETERMINATION] Home institution.** Identify the institution through which the lead researcher listed on the IRB application will conduct the research. Provide any helpful explanatory information.

In general, the home institution is the institution (1) that provides the researcher's paycheck and that considers them to be a paid employee, or (2) at which the researcher is a matriculated student. Scholars, faculty, fellows, and students who are visiting the UW and who are the lead researcher: identify your home institution and describe the purpose and duration of your UW visit, as well as the UW department/center with which you are affiliated while at the UW.

Note that many UW clinical faculty members are paid employees of non-UW institutions.

The UW IRB provides IRB review and oversight for only those researchers who meet the criteria described in the [SOP Use of the UW IRB](#).

University of Washington Medical Center

- 1.2. **[DETERMINATION] Consultation history.** Has there been any consultation with someone at HSD about this study?

It is not necessary to obtain advance consultation. However, if advance consultation was obtained, answering this question will help ensure that the IRB is aware of and considers the advice and guidance provided in that consultation.

☒ **No**

☐ **Yes** → Briefly describe the consultation: approximate date, with whom, and method (e.g., by email, phone call, in-person meeting).

Click or tap here to enter text.

- 1.3. **[DETERMINATION] Similar and/or related studies.** Are there any related IRB applications that provide context for the proposed activities?

Examples of studies for which there is likely to be a related IRB application: Using samples or data collected by another study; recruiting subjects from a registry established by a colleague's research activity; conducting Phase 2 of a multi-part project or conducting a continuation of another study; serving as the data coordinating center for a multi-site study that includes a UW site.

Providing this information (if relevant) may significantly improve the efficiency and consistency of the IRB's review.

☐ **No**

☒ **Yes** → Briefly describe the other studies or applications and how they relate to the proposed activities. If the other applications were reviewed by the UW IRB, please also provide: the UW IRB number, the study title, and the lead researcher's name.

STUDY00015475: inpatient initial insulin requirements, lead researcher [name].
This prior study built up the insulin dosing calculator that will be used in this current clinical trial.

- 1.4. **[DETERMINATION] Externally-imposed urgency or time deadlines.** Are there any externally-imposed deadlines or urgency that affect the proposed activity?

Document Date & Version

06.29.2023

Version 4.6

APPLICATION IRB Protocol

Researcher Date & Version

mm/dd/yyyy

Version x.x

Page 2 of 55

HSD recognizes that everyone would like their IRB applications to be reviewed as quickly as possible. To ensure fairness, it is HSD policy to review applications in the order in which they are received. However, HSD will assign a higher priority to research with externally-imposed urgency that is beyond the control of the researcher. Researchers are encouraged to communicate as soon as possible with their HSD staff contact person when there is an urgent situation (in other words, before submitting the IRB application). Examples: a researcher plans to test an experimental vaccine that has just been developed for a newly emerging epidemic; a researcher has an unexpected opportunity to collect data from students when the end of the school year is only four weeks away.

HSD may ask for documentation of the externally-imposed urgency. A higher priority should not be requested to compensate for a researcher's failure to prepare an IRB application in a timely manner. Note that IRB review requires a certain minimum amount of time; without sufficient time, the IRB may not be able to review and approve an application by a deadline.

☒ **No**

☐ **Yes** → Briefly describe the urgency or deadline as well as the reason for it.

Click or tap here to enter text.

- 1.5. [DETERMINATION] Objectives.** Using lay language, describe the purpose, specific aims, or objectives that will be met by this specific project. If hypotheses are being tested, describe them. You will be asked to describe the specific procedures in a later section.

If this application involves the use of a HUD “humanitarian” device: describe whether the use is for “on-label” clinical patient care, “off-label” clinical patient care, and/or research (collecting safety and/or effectiveness data).

Patients with hyperglycemia have heterogeneous physiologies and their insulin requirements are highly varied. The currently available algorithms cannot precisely predict their initial insulin doses. More importantly, there is no algorithm so far that is supported by evidence.

We hypothesize that standardized algorithms using multiple factors can more precisely predict patients' individual insulin requirements on hospital admission. Our prospective study (STUDY00015475) at the University of Washington (UW) built an insulin calculator for patients with T2DM on home insulin and adequate oral intake peri-admission (sample size 140). Using multivariable regression models, our predicted daily insulin doses have a correlation factor of 0.793 with their actual insulin requirements. No outlier that would be severely overdosed was noted in our observational cohort.

The factors used to predict insulin requirement are patients' oral intake plan, home insulin dose, first blood glucose value on presentation, inpatient glucocorticoid dose, systemic inflammatory response syndrome (SIRS), dose and timing of last long-acting insulin prior to admission. Our online calculator (<https://inpatientinsulin.com>) will be used to calculate the initial insulin dosing regimen.

Our calculator is based on observational studies, so it remains unclear whether it can help clinicians achieve recommended glycemic targets. We propose using these calculators can achieve inpatient glycemic goal of 100-180 mg/dL (American Diabetes Association's guidelines 2023) faster than the standard of care with less manual adjustments. Before we perform a study of a large sample size, it is important to test whether using this calculator in the clinical setting is safe. This study is a feasibility trial to mainly investigate its safety (no excessive hypoglycemia). We will also examine whether using this calculator decreases hyperglycemia. The trial will provide opportunities to adjust the algorithms before the randomized controlled trial.

The specific outcomes that will be measured are hypoglycemia (< 54 mg/dL), mean BG during the first 24 hours of hospitalization, and severe hyperglycemia (≥ 300 mg/dL). Hypoglycemia (< 54 mg/dL) cannot be 3% higher than the UW observational cohort (explained in section 5.1). Independent two-sample t test will be used to analyze mean BG and Pearson's chi-squared test will be used to analyze the occurrence of hyperglycemia (≥ 300 mg/dL), compared to the UW observational cohort ([STUDY00015475](#)). We plan to work with hospitalists at UW hospitals to use this calculator on hospital admissions for patients with T2DM on home insulin.

There is lack of large interventional studies to demonstrate whether improving inpatient glycemic control changes patients' clinical outcomes. The randomized controlled study we planned after this feasibility trial will explore whether using this calculator improves clinical outcomes.

- 1.6. **[DETERMINATION] Study design.** Provide a one-sentence description of the general study design and/or type of methodology.

Your answer will help HSD in assigning applications to reviewers and in managing workload. Examples: a longitudinal observational study; a double-blind, placebo-controlled randomized study; ethnographic interviews; web scraping from a convenience sample of blogs; medical record review; coordinating center for a multi-site study.

This is a clinical trial that uses the insulin dosing calculator for patients who are admitted to the UW hospitals

- 1.7. **[DETERMINATION] Intent.** Check all the descriptors that apply to your study. You must check at least one box.

This question is essential for ensuring that your application is correctly reviewed. Please read each option carefully.

Check all that apply	Descriptor
	Class project or other activity whose purpose is to provide an educational experience for the researcher (for example, to learn about the process or methods of doing research).
	Part of an institution, organization, or program's own internal operational monitoring.
	Improve the quality of service provided by a specific institution, organization, or program.
	Designed to expand the knowledge base of a scientific discipline or other scholarly field of study, and produce results that: 
• Are expected to apply to a larger population beyond the site of data collection or the specific subjects studied, or• Are intended to be used to develop, test, or support theories, principles, and statements of relationships, or to inform policy beyond the study.
	Focus directly on the specific individuals about whom the information or biospecimens are collected through oral history, journalism, biography, or historical scholarship activities, to provide an accurate and evidence-based portrayal of the individuals.
	A quality improvement or program improvement activity conducted to improve the implementation (delivery or quality) of an accepted practice, or to collect data about the implementation of the practice for clinical, practical, or administrative purposes. This does not include the evaluation of the efficacy of different accepted practices, or a comparison of their efficacy.
	Public health surveillance activities conducted, requested, or authorized by a public health authority for the sole purpose of identifying or investigating potential public health signals or timely awareness and priority setting during a situation that threatens public health.

Check all that apply	Descriptor
	Preliminary, exploratory or research development activities (such as pilot and feasibility studies, or reliability/validation testing of a questionnaire).
	Expanded access use of a drug or device not yet approved for this purpose.
	Use of a Humanitarian Use Device.
	Other. Explain:

Click or tap here to enter text.

1.8. Background, experience, and preliminary work. Answer this question only if the proposed activity has one or more of the following characteristics. The purpose of this question is to provide the IRB with information that is relevant to its risk/benefit analysis.

- Involves more than minimal risk (physical or non-physical)
- Is a clinical trial, or
- Involves having the subjects use a drug, biological, botanical, nutritional supplement, or medical device.

“Minimal risk” means that the probability and magnitude of harm or discomfort anticipated in the research are not greater than those ordinarily encountered in daily life or during the performance of routine physical or psychological examinations or tests.

1.8.a. Background. Provide the rationale and the scientific or scholarly background for the proposed activity, based on existing literature (or clinical knowledge). Describe the gaps in current knowledge that the project is intended to address.

This should be a plain language description. Do not provide scholarly citations. Limit your answer to less than one page or refer to an attached document with background information that is no more than three pages long.

The current practice of inpatient glycemic management relies heavily on daily adjustments of insulin doses based on inpatient blood glucose values. However, the real-world glycemic data analysis in the US consistently showed suboptimal results of hyperglycemia and hypoglycemia [1]. Patients with hyperglycemia have heterogenous physiologies and their insulin requirements are highly varied. The currently available algorithms cannot precisely predict their initial insulin doses [2,3]. More importantly, there is no algorithm so far that is supported by evidence. Therefore, evidence-based algorithms that can precisely predict patients’ individual insulin requirements are of benefit.

3. [name] HH, Kahn SE, Hirsch IB. Marked variability of starting insulin algorithms for noncritical illness—A survey of 32 academic hospitals in the United States. 83rd American Diabetes Association Scientific Sessions oral abstract presentation (168-OR). 2023 Jun 24, San Diego.

1.8.b. Experience and preliminary work. Briefly describe experience or preliminary work or data (if any) that you, your team, or your collaborators/co-investigators have that supports the feasibility and/or safety of this study.

It is not necessary to summarize all the discussion that has led to the development of the study protocol. The IRB is interested only in short summaries about experiences or preliminary work that suggest the study is feasible and that risks are reasonable relative to the benefits. Examples: Your team has already conducted a Phase 1 study of an experimental drug which supports the Phase 2 study being proposed in this application; your team has already done a small pilot study showing that the reading skills intervention described in this application is feasible in an after-school program with classroom aides; your team has experience with the type of surgery that is required to implant the study device; the study coordinator is experienced in working with subjects who have significant cognitive impairment.

Our proof-of-concept study at UC Davis identified several factors associated with initial insulin requirements for patients with history of diabetes mellitus (DM) and any BG value ≥ 180 mg/dL during the first 24 hours of hospitalization [1]. Then our prospective study at the University of Washington (UW) built insulin calculators for patients with different types of DM. For the study population of this trial, patients with T2DM or steroid-induced DM who take insulin prior to admission, our predicted daily insulin dose has a correlation factor of 0.795 with their actual insulin requirements. In addition, we excluded outliers (who have low oral intake before or after admission) so the rest of patients show no severe overdose in our cohort.

1. [name] HH, Surampudi P, Sood A. Determinants of initial insulin therapy for hospitalized patients with diabetes mellitus. J Diabetes Complications. 2022 Oct;36(10):108307.

1.8.c. Subject matter expertise. Is the study a clinical trial and/or does the study involve use of a drug, biologic, botanical, nutritional supplement and/or is the study otherwise considered to be greater than minimal risk to subjects?

- ☐ **No** → Answering this question is optional.
- ☒ **Yes** → Provide the name, degree(s), and contact information (e.g., email, phone number) of someone with appropriate expertise in the subject matter described in the objectives and design of this study. The individual should be unaffiliated with the study and have no other apparent conflict of interest. The individual may be associated with the UW or external to the University. Ensure the individual is aware they may be contacted by HSD.

*Provision of this information is **required** for all clinical trials, for studies involving the use of a drug, biologic, botanical, nutritional supplement and for studies involving greater than minimal risk. For all other studies, the information is optional, though HSD reserves the right to request researcher assistance in providing a consultant if necessary to complete review of the study.*

For the consultant, the request involves a brief email or phone call with targeted questions that usually can be responded to in 30 minutes or less.

[name] MD, email: [contact]

1.9. Supplements. Check all boxes that apply, to identify relevant SUPPLEMENTS that should be completed and uploaded to **Zipline**.

This section is here instead of at the end of the form to reduce the risk of duplicating information in this IRB Protocol form that you will need to provide in these Supplements.

Document Date & Version

06.29.2023

Version 4.6

APPLICATION IRB Protocol

Researcher Date & Version

mm/dd/yyyy

Version x.x

Page 6 of 55

Check all that apply	Type of Research	Supplement Name and Link
	Department of Defense The research involves Department of Defense funding, facilities, data, or personnel.	SUPPLEMENT Department of Defense
	Department of Energy The research involves Department of Energy funding, facilities, data, or personnel.	SUPPLEMENT Department of Energy
	Drug, biologic, botanical, supplement Procedures involve the use of any drug, biologic, botanical or supplement, even if the item is not the focus of the proposed research.	SUPPLEMENT Drugs
	Emergency exception to informed consent Research that requires this special consent waiver for research involving more than minimal risk.	SUPPLEMENT Exception from Informed Consent for Emergency Research (EFIC)
	Genomic data sharing Genomic data are being collected and will be deposited in an external database (such as the NIH dbGaP database) for sharing with other researchers, and the UW is being asked to provide the required certification or to ensure that the consent forms can be certified.	SUPPLEMENT Genomic Data Sharing
	Medical device Procedures involve the use of any medical device, even if the device is not the focus of the proposed research, except when the device is FDA-approved and is being used through a clinical facility in the manner for which it is approved.	SUPPLEMENT Devices
	Multi-site or collaborative study The UW IRB is being asked to review on behalf of one or more non-UW institutions in a multi-site or collaborative study.	SUPPLEMENT Multi-site or Collaborative Research
	Non-UW Individual Investigators The UW IRB is being asked to review on behalf of one or more non-UW individuals who are not affiliated with another organization for the purpose of the research.	SUPPLEMENT Non-UW Individual Investigators
	Other REDCap Installation Attestation for Electronic Consent The research will use a non-UW installation of REDCap for conducting and/or documenting informed consent.	SUPPLEMENT Other REDCap Installation
	None of the above.	

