5. PROCEDURES

5.1. [DETERMINATION] Study procedures. Using lay language, provide a complete description of the study procedures, including the sequence, intervention, or manipulation (if any), drug dosing information (if any), blood volumes and frequency of draws (if any), use of records, time required, and setting/location. If it is available: Upload a study flow sheet or table to **Zipline**.

For studies comparing standards of care: It is important to accurately identify the research procedures. Review the section titled, "When to describe risks for studies evaluating medically recognized standards of care" in the [Identifying and Describing Reasonably Foreseeable Risks in Research](#) guidance and the draft guidance from the federal Office of Human Research Protections, "[Guidance on Disclosing Reasonably Foreseeable Risks in Research Evaluating Standards of Care](#)"; October 20, 2014.

Information about pediatric blood volume and frequency of draws that would qualify for expedited review can be found in this [reference table](#) on the Seattle Children's IRB website.

We plan to work with the internal medicine hospitalist group to conduct this study. There will be two lead hospitalists of contact at Montlake, Harborview and Northwest each. The screening hospitalists screen patients who need to be admitted to the hospital as their regular practice. In the meantime, they will screen eligible subjects who meet our inclusion/exclusion criteria.

Once eligible subjects are identified, screening hospitalists or admitting hospitalists will explain the rationales of this study and obtain informed consent. This process will be part of the standard admission interview which happens within one hour of admission. The interview happens either in the emergency room or hospital room, depending on whether a hospital room is immediately available.

This feasibility trial is designed as single-arm and mainly to investigate safety (no excessive hypoglycemia compared to standard of care). We will examine hyperglycemia as a secondary endpoint. We do not include a control arm in this study for comparison. The reason is it takes too many subjects to have enough power to detect potential excessive hypoglycemia (we plan a randomized study of a larger sample size after this feasibility trial to further exam the glycemic and clinical outcomes). For a feasibility trial, we would like to know if it is safe by testing on a small number of subjects.

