We plan to extract data from the inpatient Electronic Medical Record (EMR), including demographic characteristics (age, gender, race, weight, height), diabetes history (diabetes type, home antidiabetic medications), vital signs, laboratory measurements (POC BG and laboratory venous BG, latest hemoglobin A1c, renal function), interventions (inpatient insulin dose and modality, glucocorticoid, pain medication, surgery or procedure), nutrition status (oral intake, tube feed, intravenous dextrose), and hospital admission/discharge dates.

Our UW observational cohort (STUDY00015475) has 1/140 patients (0.7%) who had hypoglycemia < 54 mg/dL during the first 24 hours of hospitalization. We think (and from prior inpatient glycemic trials) 3% increase (which means 3.7%) is considered clinically significant increase, so among these 85 subjects there cannot be more than $85 \times 3.7\% = 3.15$ subjects that develop hypoglycemia < 54 mg/dL. So, if we find more than 3.15 patients (round to 4) who develop BG < 54 during the recruitment, that is more than 3% increase. Because this is the first feasibility trial to apply the calculator on patients, we plan to enroll 10 subjects first, to demonstrate the calculator dose does not cause hypoglycemia (≤ 54 mg/dL). After these 10 participants are recruited, we will review and analyze these data. Then we will apply for a modification to increase the sample size.

To examine the feasibility, the specific outcomes that will be measured are hypoglycemia (< 54 mg/dL), mean BG during the first 24 hours of hospitalization, and hyperglycemia (≥ 300 mg/dL), compared to our UW observational cohort ([STUDY00015475](#)).

The International Hypoglycemia Study Group defined three levels of hypoglycemia for the purpose of standardized reporting: BG < 70 mg/dL (level 1), < 54 mg/dL (level 2), < 40 mg/dL (level 3) [1]. Centers for Medicare & Medicaid Services (CMS) use the same definition to capture hospital glycemic data [2]. BG < 54 mg/dL was defined as clinically significant hypoglycemia and used in prior inpatient glycemic trials [3].

For statistical analyses, trial subjects (single-arm study with utilization of the insulin calculator) will be compared with the UW observational cohort (STUDY00015475) where standard of care was used (mostly by physicians' experience). The primary endpoint is hypoglycemia < 54 mg/dL. The secondary endpoint is mean BG during the first 24 hours of hospitalization and hyperglycemia (≥ 300 mg/dL).

Reference

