- ☐ Northwest Diagnostic Imaging
- ☐ Other: identify in the text box below:

Click or tap here to enter text.

5.3.c. Personnel. For MRI scans that will be conducted at the DISC, CHN or BMIC research facilities:

Indicate who will be responsible for operating the MRI scanner by checking all that apply.

- ☐ MRI technician who is formally qualified
- ☐ Researcher who has completed scanner operator training provided by a qualified MRI operator

5.4. [DETERMINATION] Data variables. Describe the specific data that will be obtained (including a description of the most sensitive items). Alternatively, a list of the data variables may be uploaded to **Zipline**.

The factors used to predict insulin requirement are patients' oral intake plan, home insulin dose, first blood glucose value on presentation, inpatient glucocorticoid dose, systemic inflammatory response syndrome (SIRS), dose and timing of last long-acting insulin prior to admission. Our online calculator (<https://inpatientinsulin.com>) will be used to calculate the initial insulin dosing regimen.

On hospital admission, hospitalists will obtain the above data to calculate initial insulin doses: patient's current appetite and meal plan, daily insulin dose prior to admission, first blood glucose value on hospital presentation, glucocorticoid dose before and after hospital presentation, vital signs and white blood cell count, dose and timing of the last long-acting insulin prior to admission.

Data extracted from the inpatient Electronic Medical Record (EMR): demographic characteristics (age, gender, race, weight, height), diabetes history (diabetes type, home antidiabetic medications), vital signs, laboratory measurements (POC BG and laboratory venous BG, latest hemoglobin A1c, renal function), interventions (inpatient insulin dose and modality, glucocorticoid, pain medication, surgery or procedure), nutrition status (oral intake, tube feed, intravenous dextrose), and hospital admission/discharge dates.

5.5. [DETERMINATION] Data sources. For all types of data that will be accessed or collected for this research: Identify whether the data are being obtained from the subjects (or subjects' specimens) or whether they are being obtained from some other source (and identify the source).

If you have already provided this information in [Question 5.1](#), you do not need to repeat the information here.

As the above answer

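### Mean glucose and severe hyperglycemia are compared with a non-randomized earlier cohort by unadjusted tests, although the calculator's inputs should allow adjustment

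*Combined protocol and SAP*

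**What the plan says.** Section 5.1 describes a single-arm trial: "We do not include a control arm in this study for comparison". Instead, trial subjects "will be compared with the UW observational cohort (STUDY00015475) where standard of care was used". On the endpoints concerned it says: "The secondary endpoint is mean BG during the first 24 hours of hospitalization and hyperglycemia" (300 mg/dL or more).

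The only methods named for these endpoints are in Section 1.5: "Independent two-sample t test will be used to analyze mean BG and Pearson's chi-squared test will be used to analyze the occurrence of hyperglycemia". Section 5.1 repeats the comparison and adds nothing to the method. No covariate, matching, weighting, stratification or baseline comparison appears anywhere in the document.

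On the data available, Section 1.5 says the earlier study "built an insulin calculator for patients with T2DM on home insulin and adequate oral intake peri-admission (sample size 140"), using multivariable regression. Section 5.4 lists the calculator's inputs, among them home insulin dose and "first blood glucose value on presentation, inpatient glucocorticoid dose, systemic inflammatory response syndrome (SIRS"), and says that hospitalists obtain these data at admission to run the calculator.

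**The concern.** The two groups are neither randomized nor concurrent, and the documents show that they were selected differently:

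- Section 1.8.b says the cohort dropped patients with low oral intake before or after admission. Section 2.2.b excludes trial patients mainly on intake before admission, reported appetite and eating plans at admission.
- Section 5.1 requires calculator inputs that are reliable to within plus or minus 10%. No such standard is given for the cohort.
- Sections 10.1 and 10.8 keep out, or withdraw, patients for whom an overnight doubt about the calculated dose cannot be resolved. Section 10.8 also withdraws patients who received insulin before the study dose and patients who come to need IV insulin.
- Section 2.2.a admits steroid-induced diabetes. Section 1.5 describes the 140 cohort patients as having type 2 diabetes, whereas Section 1.8.b speaks of type 2 or steroid-induced diabetes.

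An unadjusted test attributes any resulting difference in first glucose, steroid exposure or home insulin dose to the calculator. Section 1.5 asks whether the calculator decreases hyperglycemia and says that the trial gives an opportunity to adjust the algorithms before a randomized trial. A case-mix artifact could mislead on both. Ignoring first glucose also gives up precision.

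**Working it through.** **The plan's own figure.** No SD, effect size, power or significance level is stated for the secondary endpoints, so there is nothing of the plan's to reproduce for them. Its one computed figure is the hypoglycemia limit: 85 × 3.7% = 3.145, given as 3.15. That reproduces, but it concerns the primary endpoint.

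**Inputs from the documents.** 85 trial subjects at most (Sections 2.9 and 5.1) and 140 cohort patients (Section 1.5).

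**Inputs assumed.** SD of 24-hour mean glucose 45 to 65 mg/dL, equal in both groups; two-sided 5% level; a between-group difference of 20 mg/dL in mean first glucose; a slope of 24-hour mean on first glucose of 0.3 to 0.5.

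**Precision of the unadjusted comparison.** SE = SD × sqrt(1/85 + 1/140) = SD × 0.1375.

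| SD (mg/dL) | SE | 95% half-width (1.97 × SE) |
|---|---|---|
| 45 | 6.2 | 12.2 |
| 55 | 7.6 | 14.9 |
| 65 | 8.9 | 17.6 |

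**Spurious difference with no true effect.** Bias = slope × imbalance = 0.3 × 20 to 0.5 × 20 = 6 to 10 mg/dL. Against the half-width this runs from 6/17.6 = 34% to 10/12.2 = 82%. The bias is proportional to the imbalance, so 10 mg/dL would give 3 to 5.

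**False-positive rate.** Let D be the imbalance in first glucose in SD units and ρ its correlation with 24-hour mean glucose. The bias is ρD in SDs of the outcome, and the rejection rate at nominal 5% is Φ(−1.96 + ρD/0.1375) + Φ(−1.96 − ρD/0.1375).

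| ρ | D = 0.1 | D = 0.3 | D = 0.5 |
|---|---|---|---|
| 0.3 | 5.5% | 10.0% | 19.4% |
| 0.5 | 6.5% | 19.4% | 44.4% |
| 0.7 | 8.0% | 33.3% | 72.1% |

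A simulation of 20,000 runs per setting gave 19% for the t test at ρ = 0.5, D = 0.3 and 33% at ρ = 0.7, D = 0.3. Regression on group and first glucose stayed at 4.8% to 5.0%. The simulated linear model was correct and first glucose was the only confounder, so this shows what adjustment can do at best.

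**Precision gained.** With ρ = 0.5 the SE is multiplied by sqrt(1 − 0.25) = 0.866, a cut of about 13% (7.56 to 6.55 at SD 55). The gain is smaller when the covariate is imbalanced between groups.

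**First stage only.** With the 10 subjects to be enrolled first, SE at SD 55 is 55 × sqrt(1/10 + 1/140) = 18.0 and the half-width about 36 mg/dL. The same 6 to 10 mg/dL is then 17% to 28% of it.

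**The 300 mg/dL endpoint.** Sections 1.5 and 5.1 attach the 24-hour window to mean glucose, and neither says whether the presenting value counts. If it does, every patient who arrives at 300 mg/dL or above has the event before the calculator can act. A logistic model with a smooth term in first glucose would then be misspecified, so the endpoint has to be defined before it is adjusted.

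**The case against.** The strongest reply is that little hangs on these comparisons. The trial is presented as a feasibility study mainly about safety, glycemic effect is secondary, a randomized trial is to follow, and the only decision rule concerns hypoglycemia. That stands, and it limits how serious the point is. It does not make an unadjusted comparison a sound answer to the question that Section 1.5 asks.

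Second, both groups were restricted on similar grounds (home insulin, adequate oral intake), which already gives partial control of case mix. That is also true, but the restrictions are not the same and leave first glucose and steroid dose free to differ.

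Third, every magnitude input beyond the two sample sizes is assumed. This stands in full: the documents show neither the size nor the direction of any imbalance.

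Fourth, adjustment cannot deal with calendar time, clinician engagement or glucose sampling. Section 5.1 says the 2-3 AM check is ordered for all trial subjects, and cohort sampling is not described. This stands and should be stated as a limitation.

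A reader might also infer that everything needed is already collected in both groups. The documents do not support that. Cohort availability of the calculator inputs is inferred from the models fitted to them, and nothing says the cohort recorded HbA1c. Nor can one infer that consent separates the groups, because the document does not say whether STUDY00015475 required it.

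**Conclusion.** The point holds for the two secondary endpoints. The plan names only unadjusted tests against a differently selected, non-randomized cohort, while the main prognostic inputs are obtained in the trial and very probably exist in the cohort. At 85 against 140, under the assumed inputs, an imbalance of 20 mg/dL in first glucose would shift the mean-glucose comparison by 6 to 10 mg/dL, about one third to four fifths of the 95% half-width. These figures show what is possible; they are not estimates of bias in this trial.

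A reader might go further and conclude that the safety conclusion, or the decision to proceed, is undermined. The documents do not support that: the hypoglycemia limit is a count rule that does not use these tests, and no decision rule is attached to the secondary endpoints. The change should be made before the groups are compared, but it does not call the primary analysis into question.

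**What to change.** - **Mean glucose.** Make the main analysis a linear regression of each patient's mean on group, first glucose, home daily insulin dose, glucocorticoid dose and SIRS, with robust standard errors. Add HbA1c only if the cohort has it.
- **Glucose of 300 mg/dL or more.** First state that values before the first inpatient insulin dose do not count, applied identically in both groups. Then report a risk difference with confidence interval adjusted for first glucose, adding glucocorticoid dose only if the number of events allows.
- **Reporting.** Show a baseline table for both groups, keep the t test and chi-squared test as supportive results, and state that adjustment covers measured differences only.
- **Before finalizing.** Confirm that the cohort file holds these variables, with compatible definitions.

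The cost is revised analysis wording, a check of the cohort data, slightly more analysis work and some dependence on the regression model. No extra trial procedure or patient is needed.
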